6.1 Interim Analyses

No interim analysis will be performed as this study was stopped prematurely.

6.2 Final Analysis

All final, planned analyses identified for Part C in the Clinical Trial Protocol and in this IAP will be performed after the last participant last visit for Part C.

7 Changes to the Planned Analyses in the Clinical Study Protocol

Only analyses of Part C of the trial are covered in this IAP. Analyses on other parts of the trial are described in separate documents.

Due to the premature discontinuation of study Part C and the low number of subjects enrolled, the scope of the statistical analysis is reduced. The table in Section 5 indicates which objectives were not addressed.

8 Analysis Populations and Subgroups

8.1 Definition of Analysis Populations

Screening Analysis Population (SCR)

The Screening analysis population includes all participants who signed the informed consent.

Full Analysis Set (FAS)/ Safety Analysis Set (SAF)

The full analysis set (FAS) will include all participants who received at least one dose of study drug. All analyses will be performed on the FAS/SAF population, or a subset thereof, as specified for a given analysis.

8.2 Subgroup Definition and Parameterization

No subgroup analyses will be performed.

9 General Specifications for Data Analyses

This section describes any general specifications to be used for the analysis. Subsequent sections may include specifications unique to that analysis, which may override the broader instructions given here.

9.1 Analysis groups

There will be 1 treatment group labelled as "M4344 250mg QD - Part C".

9.2 Presentation of Continuous and Qualitative Variables:

Continuous variables will be summarized using descriptive statistics, i.e., number of participants with non-missing values (n), mean, median, standard deviation, 25th percentile (Q1) and 75th percentile (Q3), minimum, and maximum.

Qualitative variables and rates will be summarized by frequency counts and percentages. Unless otherwise stated, the calculation of proportions will be based on the sample size of the analysis set of interest. Counts of missing observations will be included in the denominator and presented as a separate category.

If confidence intervals are to be calculated, these will be two-sided with a confidence probability of 95%, unless otherwise specified in this IAP.

Missing statistics, e.g. when they cannot be calculated, will be presented as "nd". For example, if n=1, the standard deviation cannot be computed and will be presented as "nd".

9.3 Pooling of Centers:

In order to provide overall estimates of treatment effects, data will be pooled across sites. The "site" factor will not be considered in statistical models or for subgroup analyses due to the high number of participating sites in contrast to the anticipated small number of participants treated at each site.

9.4 Definition of Baseline and Change from Baseline

In general, the last non-missing measurement prior to the first study treatment administration will be used as the baseline measurement.

If an assessment time is missing, or the study treatment start time is missing, if the assessment is planned to be performed before treatment per protocol and is performed on the same day as the start of treatment, it will be assumed that it was performed prior to treatment start. Unscheduled assessments performed on the day of study treatment are assumed to have been performed after the start of treatment if the time of the assessment or treatment start are otherwise missing.

Absolute and percent changes from baseline are defined as:

```
absolute change = visit value – baseline value
percent change = 100 * (visit value – baseline value) / baseline value
```

9.5 Unscheduled visits

Data collected at unscheduled visits will be included and analyzed for both safety and efficacy analyses in the same fashion as the data collected at scheduled visits except where otherwise noted.

9.6 Study Day

Study Day is defined relative to the date of the first administration of study treatment. Study Day 1 is defined as the day of start of study treatment; the day prior is Study Day -1 (i.e., no Study Day 0 is defined).

9.7 Definition of Duration and 'Time Since' Variables

Durations in days will be calculated by the difference of start and stop date + 1 (e.g. survival time (days) = date of death – date of randomization + 1) if not otherwise specified.

The time since an event (e.g., time since first diagnosis) will be calculated as reference date minus date of event.

9.8 Conversion Factors

The following conversion factors will be used to convert days into months or years:

$$1 \text{ week} = 7 \text{ days}, 1 \text{ month} = 30.4375 \text{ days}, 1 \text{ year} = 365.25 \text{ days}.$$

9.9 Date of Last Contact

The date of last contact will be derived for participants not known to have died at the analysis cutoff using the latest complete date prior to or at the data cut-off date among the following:

- All participant assessment dates (blood draws [laboratory, PK], vital signs, performance status, ECG, tumor assessments, quality of life assessments)
- Start and end dates of anti-cancer therapies administered after study treatment discontinuation.
- AE start and end dates
- Date of follow-up, if participant is known to be alive, as collected on the 'Follow-up' eCRF page

- Study drug start and end dates
- Date of study discontinuation if reason for discontinuation is not "Lost to follow-up"

Only dates associated with actual examinations of the participant reported in the eCRF will be used in the derivation. Dates associated with a technical operation unrelated to participant status, such as the date a blood sample was processed, will not be used.

9.10 Definition of On-treatment Period

The on-treatment period is defined as the time from the first dose of study treatment day to the last administration day of study treatment + 30 days, the data cutoff day, or death, whichever occurs first.

9.11 Imputation of Missing Data

If performed, details of imputation are specified below. If not otherwise specified, all data will be evaluated as observed, and no imputation method for missing values will be used.

In all participant data listings, imputed values will be presented, and imputed information will be flagged.

9.11.1 Incomplete Disease History Dates

Incomplete dates for disease history (e.g. initial diagnosis date, date of documented, locally advanced, inoperable or metastatic disease diagnosis, date of response or progression in prior treatment) will be imputed as follows:

- If the day is missing, it will be imputed to the 15th day of the month.
- If both day and month are missing and the year is prior to the year of the first study treatment, the month and day will be imputed as July 1st.
- If both day and month are missing and the year is the same as the year of the first study treatment, the month and day will be imputed as January 1st.

If the date is completely missing, no imputation will be performed.

9.11.2 Incomplete Adverse Events Dates

Incomplete AE-related dates are imputed for use in determining whether the AE is considered Treatment-Emergent. Incomplete dates will be imputed as follows:

- If the AE onset date is missing completely, then the onset date will be replaced by the start of study treatment.
- If only the day part of the AE onset date is missing, but the month and year are equal to the start of study treatment, then the AE onset date will be replaced by the start of study treatment. For example, if the AE onset date is --/JAN/2015, and study treatment start date is 15/JAN/2015, then the imputed AE onset date will be 15/JAN/2015. If the end date or resolution date indicates that the AE has stopped before start of treatment, this date will be used for imputation instead of start of treatment date.

- If both the day and month of the AE onset date are missing but the onset year is equal to the start of study treatment, then the onset date will be replaced by the start of study treatment. For example, if AE onset date is --/---/2014, and study treatment start date is 19/NOV/2014, then the imputed AE onset date will be 19/NOV/2014.
- In all other cases the missing onset day or missing onset month will be replaced by 1.
- Incomplete stop date will be replaced by the last day of the month (if only the day is missing),
 if not resulting in a date later than the date of participant's death. In the latter case the date of
 death will be used to impute the incomplete stop date.

In all other cases the incomplete stop date will not be imputed. If stop date of AE is after date of cut-off this date will be kept.

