15.2 Adverse Events

Analysis set: SAF

Treatment emergent adverse events (TEAEs) are defined as those events with onset dates occurring within the on-treatment period as defined in Section 9.

All analyses described in Section 15.2 will be based on TEAEs if not otherwise specified.

Incomplete AE-related dates will be handled as follows:

- In case the onset date is missing completely or missing partially but the onset month and year, or the onset year are equal to the start of trial treatment then the onset date will be replaced by the minimum of start of trial treatment and AE resolution date.
- In all other cases the missing onset day or missing onset month will be replaced by 1.
- Incomplete stop dates will be replaced by the last day of the month (if day is missing only), if
 not resulting in a date later than the date of subject's death. In the later case the date of death
 will be used to impute the incomplete stop date.
- In all other cases the incomplete stop date will not be imputed. If stop date of AE is after date
 of cut-off outcome of AE is ongoing at cut-off.

AEs will be summarized and presented based on the information collected from the "Adverse Events" eCRF page. Pretreatment AEs are defined as AEs that were reported or worsened after signature of the informed consent form up to the start of the trial drug (M4344 or carboplatin, as applicable).

- Related adverse events: adverse events with relationship to study treatment reported by the investigator and those of unknown relationship (i.e. missing data for relationship).
 - M4344: "Relationship to VX-803" (Parts A and B1) or "Relationship with M4344" (Part A2) = "Related", "Possibly Related", or missing
 - Carboplatin: "Relationship to carboplatin" = "Related", "Possibly Related", or missing
- Serious adverse events (SAEs): serious adverse events (serious adverse events = "Yes").
- AEs leading to permanent treatment discontinuation
 - M4344: "VX-803 Action Taken" (Parts A and B1) or "Action(s) taken with M4344" (Part A2) = "DrugWithdrawn"

- Carboplatin: "Carboplatin Action Taken" = "Drug Withdrawn"
- AEs leading to temporary treatment discontinuation
 - M4344: "VX-803 Action Taken" (Parts A and B1) or "Action(s) taken with M4344" (Part A2) = "Drug Interrupted"
 - Carboplatin: "Carboplatin Action Taken" = "Drug Interrupted"

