9.11.4 Incomplete End Date of Study Treatment Date

- In case the last date of study drug is missing or incomplete the date of last administration of study drug will be taken from the treatment termination eCRF pages.
- If the last date of study drug is completely missing and there is no End of Treatment eCRF
 page and no death date, study treatment should be considered to be ongoing and the cut-off
 date should be used in the analysis as the last dosing date.
- If the last date of study drug is completely or partially missing and there is either an End of Treatment eCRF page OR a death date available (within the cut-off date) then imputed last dose date is:
 - = 31DECYYYY, if only Year is available and Year < Year of min (EOT date, death date)
 - = Last day of the month, if both Year and Month are available and Year = Year of min (EOT date, death date) and Month < the month of min (EOT date, death date)
 - = min (EOT date, death date), for all other cases

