15.1 Primary Endpoint: Adverse Events

Treatment-emergent adverse events (TEAE) are those events with onset dates occurring within the on-treatment periods as defined in Section 9.10.

Adverse events related to study treatment are those events with relationship missing, unknown or yes.

Serious adverse events (SAEs) are AEs with the eCRF field "Serious adverse event" marked "Yes"

AEs leading to temporary treatment discontinuation are those with the action "Drug interrupted" selected.

AEs leading to permanent treatment discontinuation are those with "Drug withdrawn" checked as an "Action taken with M4344" on the Adverse Events eCRF page.

AEs leading to death are AEs with NCI-CTCAE toxicity Grade 5 or outcome "fatal".

All analyses described in Section 15.1 will be based on TEAEs if not otherwise specified. Separate listings will be produced for AEs outside the on-treatment period and AEs attributed to the impact of COVID-19.

Unless otherwise specified, TEAEs will be summarized by number and percentage of participants with the TEAE in the category of interest, by primary SOC, in alphabetic order, and PT in decreasing frequency for the Total column.

Each participant will be counted only once within each SOC or PT. If a participant experiences more than one AE within a given SOC or PT, only the AE with the strongest relationship or the worst severity, as appropriate, will be included in the summaries of relationship and severity.

Adverse events will be summarized by worst severity (according to NCI-CTCAE version 5.0) per participant, using the latest version of MedDRA preferred term (PT) as event category and MedDRA primary system organ class (SOC) body term as Body System category.

In case a participant has events with missing and non-missing grades, the maximum of the non-missing grades will be displayed. No imputation of missing grades will be performed.

Incomplete AE-related dates will be handled as specified in Section 9.12.2.

The following tables will be created:

- The overall summary of AEs table will include the frequency (number and percentage) of participants with each of the following:
 - TEAEs
 - TEAEs with NCI-CTCAE Grade ≥ 3, by grade
 - Related TEAEs
 - Related TEAEs with NCI-CTCAE Grade ≥ 3, by grade

- TEAEs leading to temporary treatment discontinuation
- Related TEAEs leading to temporary treatment discontinuation
- TEAEs leading to permanent treatment discontinuation
- Related TEAEs leading to permanent treatment discontinuation

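### Part C IAP: two date-imputation rules can override recorded dates, one for AEs with a fully missing or year-only onset, one for a month-only last dose in an earlier calendar year

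*SAP*

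**What the plan says.** All references are to the Part C IAP unless stated otherwise.

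**AE onset.** Section 9.11.2 gives the purpose: "Incomplete AE-related dates are imputed for use in determining whether the AE is considered Treatment-Emergent". Three of its rules set the onset to first dose:
- Onset fully missing: "If the AE onset date is missing completely, then the onset date will be replaced by the start of study treatment". No exception follows.
- Only the day missing, with month and year equal to those of treatment start: first dose, with an exception: "If the end date or resolution date indicates that the AE has stopped before start of treatment, this date will be used for imputation".
- Year only: when "both the day and month of the AE onset date are missing but the onset year is equal to the start of study treatment", the onset becomes first dose. No exception follows.

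Section 15.1 defines TEAEs as "those events with onset dates occurring within the on-treatment periods as defined in Section 9.10". Section 9.10 runs that period "from the first dose of study treatment day to the last administration day of study treatment + 30 days", cut short by data cutoff or death.

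The separate IAP for Parts A, A2 and B1 (Section 15.2) covers the same three situations in one sentence. There the onset is "replaced by the minimum of start of trial treatment and AE resolution date".

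**Last dose.** Section 9.11.4 first turns to the treatment termination eCRF pages. If the date is still incomplete and an end-of-treatment (EOT) page or a death date exists, three outcomes are possible:
- 31 December, if only the year is known and it is earlier than the year of min(EOT, death).
- "Last day of the month, if both Year and Month are available and Year = Year of min (EOT date, death date"), and the month is earlier.
- min(EOT, death) in every other case.

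**The concern.** Both rules can replace something the site recorded with a date that the record rules out.

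For AEs, the stop date alone can show that an event ended before dosing. The plan accepts this when the day is missing, but not in the two rules where the onset is known less well. A pre-treatment event is then counted as treatment-emergent, and TEAE occurrence is one of the Part C primary endpoints (Section 5).

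For the last dose, the month-end rule requires the recorded year to equal the year of min(EOT, death). A known month in an earlier year meets neither specific condition and drops to the catch-all. The last dose date sets exposure duration, planned dose and relative dose intensity (Section 13). It also sets the end of the on-treatment period (Section 9.10), which governs TEAEs and worst laboratory grades.

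**Working it through.** **1. AE onset, rules applied as written**

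The plan's two worked examples reproduce: January 2015 with first dose 15 Jan 2015 gives 15 Jan 2015, and 2014 with first dose 19 Nov 2014 gives 19 Nov 2014. The table adds an assumed stop date before first dose. The last column is the Parts A/A2/B1 rule, min(treatment start, stop date).

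| Onset recorded | First dose | Stop date (assumed) | Part C onset | Part C TEAE? | Parts A/A2/B1 onset, TEAE? |
|---|---|---|---|---|---|
| Fully missing | 15 Jan 2015 | 10 Jan 2015 | 15 Jan 2015 | Yes | 10 Jan 2015, no |
| Jan 2015, day missing | 15 Jan 2015 | 10 Jan 2015 | 10 Jan 2015 | No | 10 Jan 2015, no |
| 2014 only | 19 Nov 2014 | 10 Nov 2014 | 19 Nov 2014 | Yes | 10 Nov 2014, no |

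In the first and third rows the imputed onset falls after the event's own end, by 15 − 10 = 5 days and 19 − 10 = 9 days.

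Section 9.11.3 of the same plan does use the stop date for medications: an unknown start with a stop before treatment is classed as previous only.

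**2. Last dose, rules applied as written**

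Dates are assumed, and the termination pages are taken to give no complete date.

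| Last dose recorded | min(EOT, death) | Condition met | Imputed last dose |
|---|---|---|---|
| Nov 2020 | 20 Dec 2020 | Same year, earlier month | 30 Nov 2020 |
| Nov 2020 | 15 Jan 2021 | None | 15 Jan 2021 |
| 2020 only | 15 Jan 2021 | Year only, earlier | 31 Dec 2020 |

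Any month of 2020 with min(EOT, death) in January 2021 ends up at the January date. Knowing the month therefore gives a worse result than knowing only the year: 15 January is 46 days after 30 November, and 31 December is 31 days after it.

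**3. Size of the illustration (second row)**

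- Shift past the recorded month: 31 days of December + 15 = 46 days.
- Planned dose is cohort dose × days of exposure. At 250 mg daily (Section 9.1) the extra is 46 × 250 = 11,500 mg.
- The on-treatment period is last dose + 30 days. Its end moves from 30 Dec 2020 to 14 Feb 2021, up to 46 days more, unless cutoff or death comes first.
- Relative dose intensity: assume first dose on 1 Oct 2020, 250 mg taken every day through 30 Nov, and dose intensity as cumulative dose divided by days of exposure. Exposure to 30 Nov is 31 + 30 = 61 days (61/7 = 8.71 weeks), and relative dose intensity is 100%. Under the rule, exposure is 61 + 46 = 107 days (107/7 = 15.29 weeks), and relative dose intensity is 61/107 = 57.0%. The participant moves from the 90–110% category to the one below 60%.

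**4. Effect on a TEAE row**

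Thirteen participants were enrolled (Section 6). If all were dosed, one misclassified participant changes a row by 1/13 = 7.7 percentage points. Section 15.1 counts each participant once per SOC or PT, so this happens only where the participant has no other event in that row.

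**The case against.** The strongest case against is about reach.

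- **The last-dose gap is conditional.** The termination pages come first and would often supply a complete date. The fault acts only if they do not, the day is missing, and the recorded month lies in an earlier calendar year than min(EOT, death). This stands and limits frequency.
- **No record is shown to be affected.** The Part C IAP gives no enrolment or dosing dates. A reader might infer from a plan dated April 2021 and a protocol version dated January 2020 that treatment probably straddled 2020 and 2021. The documents do not support that, nor do they say that any last dose was recorded by month only.
- **The AE fault is narrow.** A reader might infer that AEs resolved before dosing in general become TEAEs. They do not. Complete onset dates are untouched, the missing-day rule has its check, and a partial onset placed in an earlier month or year is set to the first of that period.
- **The other IAP covers other study parts.** The difference between the two is a useful comparison, not a contradiction.
- **The error might be caught.** Imputed values are flagged in listings (Section 9.11), and a data review meeting precedes database lock (Section 6). With 13 participants, an onset after its own stop date should be noticed. This lowers the risk but leaves the rule as it is.

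None of this shows that the results are intended. Calling the AE rule a conservative convention does not fit a plan that lets the stop date prevail when only the day is missing.

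**Conclusion.** Both faults hold on the text. In Section 9.11.2, a fully missing onset, or a year-only onset in the year of treatment start, is set to first dose even when the recorded stop date precedes first dose. In Section 9.11.4, once the eCRF step has failed to give a complete date, a known month in an earlier calendar year is overridden by min(EOT, death). The plan's own missing-day check and its year-only rule for the last dose indicate drafting gaps rather than choices.

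The number of affected records is unknown and may be zero. The 46 days, 11,500 mg and 57.0% come from assumed dates and show only how far one record can move. The 7.7 points are a maximum per table row and assume that all 13 enrolled were dosed. The faults should be corrected because one of them bears directly on a primary safety endpoint and the correction is simple, not because a large effect has been shown.

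**What to change.** **Section 9.11.2.** In all three rules that impute first dose, use the earlier of treatment start and AE stop date. State what applies when the stop date is missing or cannot be imputed: use treatment start, unless the partial stop date itself shows that the AE ended before treatment (for example, a stop year earlier than the year of first dose). In that case the AE is not treatment-emergent.

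**Section 9.11.4.** Keep the eCRF step first. Then replace the same-year condition with a joint comparison: if year and month are known and that year-month is earlier than the year-month of min(EOT, death), use the last day of the recorded month. The year-only rule and the catch-all stay as they are.

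The cost is a few lines of IAP text and the matching program code. Cases the plan already handles correctly give the same result as before.

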9.11.3 Incomplete Concomitant Medication and Concurrent Procedure Dates

For identification of previous or concomitant medications/procedures, no formal imputation will be performed on missing or incomplete dates. Rules presented in Table 2 will be used to define if a medication/procedure is considered as a previous, concomitant or both previous and concomitant medication/procedure, based on the stopping rules presented in Table 1.

Table 1 Stopping rules for medication/procedure end dates

End date of medication/procedure		e of medication/procedure	Stopping rule		
Day Month Year		Year			
UNK	UNK	UNK	After treatment start (ongoing)		
UNK	UNK	< Treatment start (year)	Before treatment start		
UNK	UNK >= Treatment start (year)		After treatment start		
UNK	K < Treatment start (month and year)		Before treatment start		
UNK	JNK >= Treatment start (month and year)		After treatment start		
< Treatment start (complete date)		(complete date)	Before treatment start		
>= Treatment start (complete date)		rt (complete date)	After treatment start		

UNK = Unknown

Table 2 Rules to define previous and/or concomitant medication

Start date of medication/procedure		of medication/procedure Stopping rule (see Table 1)		Medication/procedure
Day	Month	Year		
UNK	UNK	UNK	Before treatment start	Previous
UNK	UNK	UNK	After treatment start	Previous and concomitant
UNK	UNK	<= Treatment start (year)	Before treatment start	Previous
UNK	UNK	<= Treatment start (year)	After treatment start	Previous and concomitant

Start date of medication/procedure			Stopping rule (see Table 1)	Medication/procedure
Day	Month	Year		
UNK	UNK	> Treatment start (year) and <= Treatment end + 28 days (year)	After treatment start	Concomitant
UNK	UNK <= Treatment start (month and year)		Before treatment start	Previous
UNK	NK <= Treatment start (month and year)		After treatment start	Previous and concomitant
> Treatment start (month and year) and <= UNK Treatment end + 28 days (month and year)			After treatment start	Concomitant
<= Trea	tment start	(date)	Before treatment start	Previous
<= Treatment start (date)			After treatment start	Previous and concomitant
> Treatment start (date) and <= Treatment end + 28 days (date)			After treatment start	Concomitant

UNK = Unknown

